10.11.8.6.4. Visit 602 – 1-Week Follow-Up Visit (6-8 Days After Visit 601)

- Record AEs as described in Section 8.3.
- Review the participant's reactogenicity e-diary data. Collect stop dates of any reactogenicity e-diary events ongoing on the last day that the reactogenicity e-diary was completed and record stop dates in the CRF if required.
- Record nonstudy vaccinations as described in Section 6.8.
- Record details of any of the prohibited medications specified in Section 6.8.1 received by the participant if required for his or her clinical care.
- Discuss contraceptive use as described in Section 5.3.
- Collect a blood sample for immunogenicity testing.
- If the participant is part of the group for description of cell-mediated immune response (select sites only), collect a blood sample (approximately 120 mL) for PBMC isolation.
- Ask the participant to contact the site staff or investigator if the participant experiences acute chest pain, shortness of breath, or palpitations (see Section 10.11.8.6.12).

- Ask the participant to contact the site staff or investigator if a medically attended event (eg, doctor's visit, emergency room visit) or hospitalization occurs.
- Ask the participant to contact the site staff or investigator (this could be via the COVID-19 illness e-diary) immediately if the participant experiences any respiratory symptoms as detailed in Section 10.11.8.6.9.
- Ensure the participant has a self-swab kit.
- Schedule an appointment for the participant to return for the next study visit.
- Complete the source documents.
- The investigator or an authorized designee completes the CRFs.
- The investigator or appropriately qualified designee reviews the reactogenicity e-diary data online following vaccination to evaluate participant compliance and as part of the ongoing safety review. Daily review is optimal during the active diary period.

10.11.8.6.5. Visit 603 – 1-Month Follow-Up Visit (28 to 35 Days After Visit 601)

- Record AEs as described in Section 8.3.
- Review the participant's reactogenicity e-diary data. Collect stop dates of any reactogenicity e-diary events ongoing on the last day that the reactogenicity e-diary was completed and record stop dates in the CRF if required.
- Record nonstudy vaccinations as described in Section 6.8.
- Record details of any of the prohibited medications specified in Section 6.8.1 received by the participant if required for his or her clinical care.
- For participants who are HIV-positive, record the latest CD4 count and HIV viral load.
- Discuss contraceptive use as described in Section 5.3.
- Collect a blood sample for immunogenicity testing.
- If the participant is part of the group for description of cell-mediated immune response (select sites only), collect a blood sample (approximately 120 mL) for PBMC isolation.
- Ask the participant to contact the site staff or investigator if a medically attended event (eg, doctor's visit, emergency room visit) or hospitalization occurs.
- Ask the participant to contact the site staff or investigator (this could be via the COVID-19 illness e-diary) immediately if the participant experiences any respiratory symptoms as detailed in Section 10.11.8.6.9.

- Ensure the participant has a self-swab kit.
- Schedule an appointment for the participant to return for the next study visit.
- Complete the source documents.
- The investigator or an authorized designee completes the CRFs.
- Record any AEs that occur within the 48 hours after the blood draw as described in Section 8.3.

10.11.8.6.6. Visit 604 – 3-Month Follow-Up Visit (85 to 95 Days After Visit 601)

- Record AEs as described in Section 8.3.
- Collect a blood sample for immunogenicity testing.
- If the participant is part of the group for description of cell-mediated immune response (select sites only), collect a blood sample (approximately 120 mL) for PBMC isolation.
- Record nonstudy vaccinations as described in Section 6.8.
- Record details of any of the prohibited medications specified in Section 6.8.1 received by the participant if required for his or her clinical care.
- For participants who are HIV-positive, record the latest CD4 count and HIV viral load.
- Ask the participant to contact the site staff or investigator (this could be via the COVID-19 illness e-diary) immediately if he or she experiences any respiratory symptoms as detailed in Section 10.11.8.6.9.
- Ensure the participant has a self-swab kit.
- Schedule an appointment for the participant to return for the next study visit.
- Complete the source documents.
- The investigator or an authorized designee completes the CRFs.
- Record any AEs that occur within the 48 hours after the blood draw as described in Section 8.3.

10.11.8.6.7. Visit 605 – 6-Month Follow-Up Visit (175 to 189 Days After Visit 601)

- Record AEs as described in Section 8.3.
- Collect a blood sample for immunogenicity testing.
- If the participant is part of the group for description of cell-mediated immune response (select sites only), collect a blood sample (approximately 120 mL) for PBMC isolation.
- Record nonstudy vaccinations as described in Section 6.8.
- Record details of any of the prohibited medications specified in Section 6.8.1 received by the participant if required for his or her clinical care.
- For participants who are HIV-positive, record the latest CD4 count and HIV viral load.
- Collect the participant's e-diary or assist the participant to remove the study application from his or her own personal device.
- Complete the source documents.
- The investigator or an authorized designee completes the CRFs.
- Record any AEs that occur within the 48 hours after the blood draw as described in Section 8.3.

10.11.8.6.8. COVID-19 Surveillance (All Substudy E Participants)

If a participant experiences any of the following (irrespective of perceived etiology or clinical significance), he or she is instructed to contact the site immediately and, if confirmed, participate in an in-person or telehealth visit as soon as possible, optimally within 3 days of symptom onset (and at the latest 4 days after symptom resolution).

- A diagnosis of COVID-19;
- Fever;
- New or increased cough;
- New or increased shortness of breath;
- Chills;
- New or increased muscle pain;
- New loss of taste/smell;
- Sore throat;

- Diarrhea;
- Vomiting.

Note that:

- If new symptoms are reported within 4 days after resolution of all previous symptoms, they will be considered as part of a single illness and a second illness visit is not required;
- Surveillance of potential COVID-19 symptoms should continue even if a participant has a positive SARS-CoV-2 test earlier in the study.

During the 7 days following each vaccination, potential COVID-19 symptoms that overlap with specific systemic events (ie, fever, chills, new or increased muscle pain, diarrhea, vomiting) should not trigger a potential COVID-19 illness visit unless, in the investigator's opinion, the clinical picture is more indicative of a possible COVID-19 illness than vaccine reactogenicity. If, in the investigator's opinion, the symptoms are considered more likely to be vaccine reactogenicity, but a participant is required to demonstrate that he or she is SARS-CoV-2—negative, a local SARS-CoV-2 test may be performed: if positive, the symptoms should be recorded as a potential COVID-19 illness; if not, the symptoms should be recorded as AEs.

Participants may utilize a COVID-19 illness e-diary through an application (see Section 10.11.8.6.10) installed on a provisioned device or on the participant's own personal device to prompt him/her to report any symptoms. Note that this does not substitute for a participant's routine medical care. Therefore, participants should be encouraged to seek care, if appropriate, from their usual provider.

10.11.8.6.9. Potential COVID-19 Illness Visit (Optimally Within 3 Days After Potential COVID-19 Illness Onset)

This visit may be conducted as an in-person or telehealth visit; a telehealth visit involves the sharing of healthcare information and services via telecommunication technologies (eg, audio, video, video-conferencing software) remotely, thus allowing the participant and investigator to communicate on aspects of clinical care.

As a participant's COVID-19 illness may evolve over time, several contacts may be required to:

- Record AEs, as appropriate as described in Section 8.3. Note: Potential COVID-19 illnesses that are consistent with the clinical endpoint definition should not be recorded as AEs. These data will be captured as efficacy assessment data only on the relevant pages of the CRF, as these are expected endpoints.
- Record details of any of the prohibited medications specified in Section 6.8 received by the participant if required for his or her clinical care.

- If the visit is conducted in person, obtain a nasal (midturbinate) swab (collected by site staff). Alternatively, if the visit is conducted by telehealth, instruct the participant to self-collect a nasal (midturbinate) swab and ship for assessment at the central laboratory.
- Collect COVID-19—related standard-of-care clinical and laboratory information. This includes, but is not limited to:
 - Symptoms and signs, including
 - Clinical signs at rest indicative of severe systemic illness (RR ≥30 breaths per minute, HR ≥125 beats per minute, SpO₂ ≤93% on room air at sea level, or PaO₂/FiO₂ <300 mm Hg);
 - Evidence of shock (SBP <90 mm Hg, DBP <60 mm Hg, or requiring vasopressors);
 - Significant acute renal, hepatic, or neurologic dysfunction;
 - Respiratory failure (defined as needing high-flow oxygen, noninvasive ventilation, mechanical ventilation, or ECMO).
 - Clinical diagnosis.
 - Local laboratory SARS-CoV-2 test result(s). Note that if it is routine practice to perform a repeat local SARS-CoV-2 test for any reason, then a repeat nasal (midturbinate) swab should also be obtained and shipped for assessment at the central laboratory.
 - Full blood count.
 - Blood chemistry, specifically creatinine, urea, LFTs, and C-reactive protein.
 - Imaging results (eg, CT or MRI scan) to document neurologic dysfunction.
 - Number and type of any healthcare contact; duration of hospitalization and ICU stay.
 - Death.
- Complete the source documents.
- The investigator or an authorized designee completes the CRFs.

10.11.8.6.10. Communication and Use of Technology

In a study of this nature that requires illness events to be reported outside of scheduled study visits, it is vital that communication between the study site and the participant is maintained to ensure that endpoint events are not missed. This study will employ various methods, tailored to the individual participant, to ensure that communication is maintained and study information can be transmitted securely. Using appropriate technology, such as a study application, a communication pathway between the participant and the study site staff will be established. The participant may be able to utilize his or her own devices to access this technology, or use a device provided by the sponsor. Traditional methods of telephone communication will also be available. The technology solution may facilitate the following:

- Contact with the investigator, including the ability of the participant to report whether or not the participant has experienced symptoms that could represent a potential COVID-19 illness (COVID-19 illness e-diary).
- An alert in the event that the participant is hospitalized.
- Visit reminders.
- Messages of thanks and encouragement from the study team.
- If a participant is not actively completing the COVID-19 illness e-diary, the investigator or designee is required to contact the participant to ascertain why and also to obtain details of any missed events.

10.11.8.6.11. SARS-CoV-2 NAAT Results

Nasal (midturbinate) swabs for SARS-CoV-2 NAAT are obtained at:

- Visit 601: To determine whether a participant will be included in efficacy analyses of those with no serological or virological evidence of past SARS-CoV-2 infection.
- Potential COVID-19 illness visits: To determine whether symptoms experienced by the participant fulfill the COVID-19 case definition.

Research laboratory—generated positive results from the Visit 601 swab, and all results from the illness visit swabs, will be provided to the site once available, but this will not be in real time and cannot be relied upon to direct clinical care. Therefore, the participant should be directed to seek additional testing through his/her primary healthcare providers at a licensed clinical laboratory when exhibiting potential COVID-19 symptoms or otherwise receiving a positive result and counseled on whether to take any precautionary measures pending confirmatory testing.

10.11.8.6.12. Additional Procedures for Monitoring of Potential Myocarditis or Pericarditis

Any study participant who reports acute chest pain, shortness of breath, palpitations, or any other symptom(s) that might be indicative of myocarditis or pericarditis within 4 weeks after a study vaccination should be specifically evaluated, preferably by a cardiologist, for possible myocarditis or pericarditis. In addition to a clinical evaluation, the following should be performed:

- ECG and
- Measurement of the troponin level

If myocarditis or pericarditis is suspected based upon the initial evaluation, the following should also be performed:

- Cardiac echocardiogram and/or
- Cardiac magnetic resonance study

Details of the symptoms reported, and results of the investigations performed, will be recorded in the CRF.

10.11.8.6.13. Unscheduled Visit for a Grade 3 or Suspected Grade 4 Reaction

If a Grade 3 local reaction (Section 8.2.4.2), systemic event (Section 8.2.4.3), or fever (Section 8.2.4.4) is reported in the reactogenicity e-diary, a telephone contact should occur to ascertain further details and determine whether a site visit is clinically indicated. If a suspected Grade 4 local reaction (Section 8.2.4.2), systemic event (Section 8.2.4.3), or fever (Section 8.2.4.4) is reported in the reactogenicity e-diary, a telephone contact or site visit should occur to confirm whether the event meets the criteria for Grade 4.

A site visit must be scheduled as soon as possible to assess the participant unless any of the following is true:

- The participant is unable to attend the unscheduled visit.
- The local reaction/systemic event is no longer present at the time of the telephone contact.
- The participant recorded an incorrect value in the reactogenicity e-diary (confirmation of a reactogenicity e-diary data entry error).
- The PI or authorized designee determined it was not needed.

This telephone contact will be recorded in the participant's source documentation and the CRF.

If the participant is unable to attend the unscheduled visit, or the PI or authorized designee determined that it was not needed, any ongoing local reactions/systemic events must be assessed at the next study visit.

During the unscheduled visit, the reactions should be assessed by the investigator or a medically qualified member of the study staff, such as a study physician or a study nurse, as applicable to the investigator's local practice, who will:

- Measure body temperature (°F/°C).
- Measure minimum and maximum diameters of redness (if present).
- Measure minimum and maximum diameters of swelling (if present).
- Assess injection site pain (if present) in accordance with the grades provided in Section 8.2.4.2.
- Assess systemic events (if present) in accordance with the grades provided in Section 8.2.4.3.
- Assess for other findings associated with the reaction and record on the AE page of the CRF, if appropriate.

The investigator or an authorized designee will complete the unscheduled visit assessment page of the CRF.

10.11.9. Statistical Considerations for Substudy E

See Section 9 for master protocol statistical considerations, and see substudy specifics below.

10.11.9.1. Statistical Hypotheses

10.11.9.1.1. Estimands

The estimands corresponding to the primary and exploratory objectives are described in the table in Section 10.11.3.

In the primary safety objective evaluations, missing AE start dates will be imputed according to Pfizer safety rules. No other missing information will be imputed in the safety analysis.

10.11.9.1.2. Statistical Hypotheses

The primary and secondary immunogenicity objectives for participants >55 years of age will be evaluated by the following statistical hypotheses. The immunogenicity objectives for participants 18 through 55 years are descriptive only.

Superiority and Noninferiority of Anti-Omicron Immune Responses

The primary immunogenicity objectives are to assess the superiority with respect to level of neutralizing titer and noninferiority with respect to seroresponse rate of the anti-Omicron immune response induced by a dose of BNT162b2 OMI (30 µg or 60 µg) or bivalent BNT162b2 and BNT162b2 OMI (30 µg or 60 µg) relative to the anti-Omicron immune response elicited by a dose of BNT162b2 at 30 µg given as a fourth dose in BNT162b2-experienced participants >55 years of age. Each primary objective will be evaluated by the following 2 hypotheses:

• The first null hypothesis (H₀) is

$$H_0: \ln(\mu_1) - \ln(\mu_2) \le \ln(1) \text{ vs } H_1: \ln(\mu_1) - \ln(\mu_2) > \ln(1)$$

where ln(2) corresponds to a 1-fold superiority criterion and

- o $\ln(\mu_1)$ is the natural log of the geometric mean of SARS-CoV-2 Omicron-neutralizing titers measured 1 month after 1 dose of BNT162b2 OMI or bivalent BNT162b2 and BNT162b2 OMI given as a fourth dose;
- o $\ln(\mu_2)$ is the natural log of the geometric mean of SARS-CoV-2 Omicron-neutralizing titers measured 1 month after 1 dose of BNT162b2 at 30 µg given as a fourth dose (Group 1).
- The second null hypothesis (H₀) is

H₀:
$$p_1 - p_2 \le -0.05$$
 vs $p_1 - p_2 > -0.05$

where -5% is the noninferiority margin for seroresponse and

- o p_1 is the percentage of participants with seroresponse to the Omicron strain at 1 month after 1 dose of BNT162b2 OMI or bivalent BNT162b2 and BNT162b2 OMI given as a fourth dose;
- o p_2 is the percentage of participants with seroresponse to the Omicron strain at 1 month after 1 dose of BNT162b2 at 30 µg given as a fourth dose (Group 1).

Seroresponse is defined as achieving a \geq 4-fold rise from baseline (before the first dose of study vaccination). If the baseline measurement is below the LLOQ, the postvaccination measure of \geq 4 × LLOQ is considered seroresponse.

Superiority will be declared if the lower limit of the 2-sided 95% CI for the GMR is greater than 1; noninferiority based on seroresponse will be declared if the lower limit of the 2-sided 95% CI for the difference in percentages of participants with seroresponse is >-5%.

The secondary objective of "super" superiority will be evaluated using a 1.5-fold margin for GMR. "Super" superiority for GMR will be established if the lower limit of the 2-sided 95% CI for the GMR is greater than 1.5.

Noninferiority of Anti-Reference Strain Immune Responses

The noninferiority immunogenicity objectives on anti–reference strain immune responses are to assess the noninferiority of the anti–reference strain immune response induced by a dose of bivalent BNT162b2 and BNT162b2 OMI (30 µg or 60 µg) relative to the anti–reference strain immune response elicited by a dose of BNT162b2 at 30 µg given as a fourth dose in BNT162b2-experienced participants >55 years of age. Each noninferiority objective will be evaluated by the following hypothesis:

• The null hypothesis (H₀) is

$$H_0: \ln(\mu_1) - \ln(\mu_2) \le \ln(0.67) \text{ vs } H_1: \ln(\mu_1) - \ln(\mu_2) > \ln(0.67)$$

where ln(0.67) corresponds to a 1.5-fold margin for noninferiority and

- ln(μ₁) is the natural log of the geometric mean of SARS-CoV-2 reference-strain-neutralizing titers measured 1 month after 1 dose of bivalent BNT162b2 and BNT162b2 OMI (30 μg or 60 μg) given as a fourth dose (Group 5 or Group 6);
- o $ln(\mu_2)$ is the natural log of the geometric mean of SARS-CoV-2 reference-strain—neutralizing titers measured 1 month after 1 dose of BNT162b2 given as a fourth dose (Group 1).

Noninferiority based on the GMR will be declared if the lower limit of the 2-sided 95% CI for the GMR is greater than 0.67 (1.5-fold criterion) and the point estimate of the GMR is >0.8.

10.11.9.1.3. Multiplicity Adjustment

The primary and secondary immunogenicity objectives for participants >55 years of age will be assessed using the expanded-enrollment cohort.

The primary and secondary immunogenicity objectives for participants >55 years of age will be evaluated in sequential order as listed below using a 1-sided alpha of 0.025:

- Superiority in GMR and noninferiority in seroresponse rate for Omicron response: G4vG1A (OMI-60) → G6vG1A (bivalent-60) → G5vG1A (bivalent-30) →
- Noninferiority in GMR for reference strain response: G6vG1B (bivalent-60) → G5vG1B (bivalent-30) →
- "Super" superiority in GMR for Omicron response: G4vG1B (OMI-60) → G6vG1C (bivalent-60) → G5vG1C (bivalent-30) →
- Superiority in GMR and noninferiority in seroresponse rate for Omicron response: G3vG1A (OMI-30) → G3vG1B (OMI-30)

For objectives involving 2 hypotheses, hypotheses based on GMR and seroresponse rate difference will be assessed sequentially in the order as stated. Both hypotheses within the objective must be established before assessing the next objective in the sequence. Therefore, the overall type I error is fully controlled.

The immunogenicity objectives for participants 18 through 55 years of age are descriptive only; therefore, no multiplicity adjustment is applied.

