| G3vG1A: To demonstrate the superiority with respect to level of neutralizing titer and noninferiority with respect to seroresponse rate of anti-Omicron immune response after 1 dose of BNT162b2 OMI at 30 µg compared to after 1 dose of BNT162b2 at 30 µg given as a fourth dose in BNT162b2-experienced participants >55 years of age | In participants complying with the key protocol criteria (evaluable participants) and no serological or virological evidence (up to 1 month after receipt of 1 dose of study intervention given as a fourth dose) of past SARS-CoV-2 infection: • GMR of the Omicron-neutralizing titers at 1 month after 1 dose of BNT162b2 OMI at 30 µg to those at 1 month after 1 dose of BNT162b2 at 30 µg given as a fourth dose in BNT162b2-experienced participants • The difference in percentages of participants with seroresponse to the Omicron strain at 1 month after 1 dose of BNT162b2 OMI 30 µg and at 1 month after 1 dose of BNT162b2 at 30 µg given as a fourth dose in BNT162b2 at 30 µg given as a fourth dose in BNT162b2-experienced participants | SARS-CoV-2 Omicron-neutralizing titers |

| Objectives | Estimands | Endpoints |
|--|---|--|
| G4vG1A: To demonstrate the superiority with respect to level of neutralizing titer and noninferiority with respect to seroresponse rate of anti-Omicron immune response after 1 dose of BNT162b2 OMI at 60 μg compared to after 1 dose of BNT162b2 at 30 μg given as a fourth dose in BNT162b2-experienced participants >55 years of age | In participants complying with the key protocol criteria (evaluable participants) and no serological or virological evidence (up to 1 month after receipt of 1 dose of study intervention given as a fourth dose) of past SARS-CoV-2 infection: • GMR of the Omicron-neutralizing titers at 1 month after 1 dose of BNT162b2 OMI at 60 μg to those at 1 month after 1 dose of BNT162b2 at 30 μg given as a fourth dose in BNT162b2-experienced participants • The difference in percentages of participants with seroresponse to the Omicron strain at 1 month after 1 dose of BNT162b2 OMI 60 μg and at 1 month after 1 dose of BNT162b2 at 30 μg given as a fourth dose in BNT162b2 at 30 μg given as a fourth dose in BNT162b2-experienced participants | SARS-CoV-2 Omicron-neutralizing titers |

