10.11.9.5. Sample Size Determination

The sample size in each group is based on consideration of an acceptable safety database. For the >55-year age group, a random sample of 230 participants will be selected from each group in the expanded-enrollment cohort as an immunogenicity subset to evaluate the primary and secondary immunogenicity objectives. Assuming a 35% nonevaluable or prior infection rate, approximately 150 evaluable participants in each group will contribute to the primary immunogenicity evaluation.

Superiority and Noninferiority of Anti-Omicron Immunogenicity Objectives

For comparisons based on GMR, assuming common assay standard deviations of 1.05 in log scale based on data observed in the Phase 2 part of the C4591001 study for participants 56 years of age or older and adjusted for assay variability, if the true GMR is 1.5, with 150 evaluable participants, the study will have 91.5% power to demonstrate superiority. If the true GMR is 2.0, the study will have 65.7% power to declare "super" superiority using a 1.5-fold margin.

For comparisons based on seroresponse rate difference, if the seroresponse rate is 70% in the BNT162b2 OMI (30 μ g or 60 μ g) or bivalent BNT162b2 and BNT162b2 OMI (30 μ g or 60 μ g) group and 55% in the BNT162b2 30 μ g group, the study will have 94.9% power to demonstrate noninferiority using a 5% margin.

Noninferiority of Anti-Reference Strain Immunogenicity Objectives

For comparisons based on GMR, common assay standard deviations of 1.05 and a GMR of 1 are assumed for each comparison. With 150 evaluable participants and the stated assumptions for the GMR and standard deviation, the study has 90.9% power to demonstrate noninferiority based on the GMR using a 1.5-fold margin.

For safety outcomes, Table 14 shows the probability of observing at least 1 AE for a given true event rate of a particular AE, for various sample sizes. For example, if the true AE rate is 1%, with 300 participants in a vaccine group, there is 95% probability of observing at least 1 AE.

Table 14. Substudy E – Probability of Observing at Least 1 AE by Assumed True Event Rates With Different Sample Sizes

| Assumed True Event Rate of an AE | N=20 | N=300 | N=900 | N=1920 |
|-------------------------------------|-------|-------|-------|--------|
| 0.01% | 0.002 | 0.03 | 0.09 | 0.17 |
| 0.02% | 0.004 | 0.06 | 0.16 | 0.32 |
| 0.05% | 0.01 | 0.14 | 0.36 | 0.62 |
| 0.10% | 0.02 | 0.26 | 0.59 | 0.85 |
| 0.20% | 0.04 | 0.45 | 0.84 | 0.98 |

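### Substudy E: primary objective G3vG1A is tested ninth of ten, behind three 'super' superiority tests, so the 91.5% power quoted for superiority is not the chance that it can be formally declared

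*Protocol*

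**What the plan says.** Section 10.11.3 lists four primary immunogenicity objectives for participants over 55 years, each against Group 1 (BNT162b2 30 µg). One of them is "G3vG1A: To demonstrate the superiority with respect to level of neutralizing titer and noninferiority with respect to seroresponse rate". Each has two parts: superiority on the Omicron GMR and noninferiority on the seroresponse rate. The 'super' superiority objectives stand in the same table under secondary immunogenicity. Section 10.11.9.1.2 also calls them secondary and requires the lower 95% limit of the GMR to exceed 1.5.

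Section 10.11.9.1.3 has all of these "evaluated in sequential order as listed below using a 1-sided alpha of 0.025", with the rule that "Both hypotheses within the objective must be established before assessing the next objective in the sequence". The order is:

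- Steps 1–3, primary: G4vG1A, G6vG1A, G5vG1A.
- Steps 4–5, secondary, reference-strain noninferiority: G6vG1B, G5vG1B.
- Steps 6–8, secondary, 'super' superiority: "G4vG1B (OMI-60) → G6vG1C (bivalent-60) → G5vG1C (bivalent-30").
- Step 9, primary: "Superiority in GMR and noninferiority in seroresponse rate for Omicron response: G3vG1A (OMI-30").
- Step 10, secondary: G3vG1B.

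On power, Section 10.11.9.5 says that "if the true GMR is 1.5, with 150 evaluable participants, the study will have 91.5% power to demonstrate superiority". It gives 65.7% for 'super' superiority at a true GMR of 2.0, 94.9% for seroresponse noninferiority and 90.9% for reference-strain noninferiority. It does not mention the testing order.

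**The concern.** The label and the rank of G3vG1A disagree. As a primary objective it should carry one of the trial's main claims, yet that claim depends on five secondary objectives. Three of those are the hardest tests in the plan, powered at only 65.7% each under a more favourable assumption (GMR 2.0) than the one behind the 91.5%.

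The assumption used to power superiority, a true GMR of 1.5, is also exactly the 'super' superiority margin. If it holds in all test arms, the null hypotheses at steps 6 to 8 are true and the chain is expected to stop there. Someone using Section 10.11.9.5 to judge what the substudy can conclude about OMI 30 µg would then be badly misled.

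**Working it through.** **Inputs from Section 10.11.9.5:** 150 evaluable per group, log-scale SD 1.05, seroresponse 70% vs 55%, reference-strain GMR 1. **From Sections 10.11.9.1.2 and 10.11.9.1.3:** the margins, the extra rule that the reference-strain GMR estimate exceed 0.8, 1-sided alpha 0.025, and the order.

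**Assumptions not in the protocol:** the correlation between Omicron and reference-strain titres (0.5, varied from 0 to 0.8); seroresponse drawn independently of titre; the same GMR in all four test arms unless stated.

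**1. The protocol's own figures.** The standard error of a log GMR is 1.05 × √(2/150) = 0.1212. Noncentral t with 298 df gives:

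- Superiority at GMR 1.5: ln(1.5)/0.1212 = 3.34, power 91.5%.
- 'Super' superiority at GMR 2.0: ln(2.0/1.5)/0.1212 = 2.37, power 65.7%.
- Reference-strain noninferiority at GMR 1: −ln(0.67)/0.1212 = 3.30, power 90.9%.

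All three agree with the text. A Wald approximation for seroresponse gives 95.2% against the stated 94.9%.

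**2. The 'super' gates at GMR 1.5.** The standardised distance from the margin is ln(1.5/1.5)/0.1212 = 0, so each gate passes with probability 2.5%. That caps the power for G3vG1A at 2.5%, whatever is assumed about correlation or seroresponse. The three comparisons share Group 1, so with equal group sizes their statistics correlate at 0.5, and all three pass together with probability 0.16%. Independent gates would give 0.025³ = 0.0016%.

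**3. The whole chain through G3vG1A.** This was simulated with 1,000,000 trials per setting, covering the GMR, seroresponse and reference-strain tests. Correlation is 0.5 and seroresponse 70% vs 55%:

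| True GMR, all test arms | Steps 1–3 all passed | G3vG1A declared, present order | G3vG1A declared if placed after step 5 |
|---|---|---|---|
| 1.5 | 72% | about 0.1% | 59% |
| 1.75 | 87% | 6% | 72% |
| 2.0 | 88% | 33% | 72% |
| 2.5 | 88% | 71% | 73% |

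Varying the correlation from 0 to 0.8 moves the present-order column to 0.12–0.14%, 5–6%, 30–35% and 70–72%. Using normal rather than t limits shifts the entry at 2.0 by less than one percentage point. If test-arm seroresponse is instead assumed to be 80% at GMR 2.0 and 85% at 2.5, the present order gives about 39% and 83%.

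**4. What moving G3vG1A would cost.** All three 'super' tests would then depend on OMI-30. The probability of completing that block changes as follows:

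- GMR 2.0 in every arm, seroresponse 70% vs 55%: from about 34% to 33%.
- OMI-30 weaker (assumed GMR 1.5, 65% seroresponse; other test arms GMR 2.0, 75%): from about 38% to 29%.

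**The case against.** The best defence is that this is a legitimate, deliberate ordering. A fixed sequence needs only to be prespecified; nothing requires every primary objective to precede every secondary one. G3vG1A stands on its own line after the 60 µg and bivalent comparisons, which looks like a sponsor priority. Section 10.11.9.3.2 has the GMR, the seroresponse difference and their intervals calculated for every primary estimand, so the gate withholds only the formal claim. All of this stands.

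It is also fair that 91.5% is introduced for GMR comparisons in general and is right as a per-comparison power for the GMR hypothesis. A reader might infer that the calculation is wrong or that type I error is inflated. Neither follows: the figure reproduces, and the sequence controls the error rate.

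Finally, 0.1% belongs to one scenario, with every arm exactly on the 'super' margin. A reader might infer that G3vG1A can almost never be tested. At the protocol's own 'super' assumption of GMR 2.0 it is declared in about a third of trials, and at 2.5 in about 71%.

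The defence does not remove the mismatch. If OMI-30 was deliberately ranked low, the primary label is wrong. And 91.5% is the only superiority power given, with nothing to say that it ignores the order.

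**Conclusion.** The point holds as a mismatch between label, rank and stated power. Under the assumption behind the 91.5% (GMR 1.5 in all test arms), G3vG1A can be formally declared in about 0.1% of trials. The cap of 2.5% needs only that the arms tested for 'super' superiority have a true GMR of 1.5. The values at higher GMRs rest on 70% vs 55% seroresponse, reference-strain GMR 1 and the assumed correlation of 0.5; higher test-arm seroresponse raises them.

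It might also be inferred that moving G3vG1A forward is a free correction. It is not, because the 'super' claims, two of them bivalent, would then wait on OMI-30.

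**What to change.** In Section 10.11.9.5, state that 91.5% is per comparison, covers the GMR hypothesis only and takes no account of the sequence. Add the power along the sequence for each primary objective, with its assumptions. At GMR 1.5 this is about 72% for passing all three leading primary objectives and about 0.1% for G3vG1A as now ordered.

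If the present order is kept, reclassify G3vG1A as secondary in Section 10.11.3. Its seroresponse criterion must then be carried into Section 10.11.9.3.3, which currently describes only GMR criteria for secondary objectives. These are wording changes: no participants are added and the error control is untouched.

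The alternative, if OMI-30 is to remain primary, is to place G3vG1A after G5vG1B and before the 'super' block, leaving G3vG1B last. Its success rises to about 59% at GMR 1.5 and about 72% at 1.75 to 2.0 under 70% vs 55% seroresponse, and type I error stays controlled. The sponsor should weigh this against the loss shown for the 'super' block, which is about one percentage point if OMI-30 matches the other arms and about nine in the weaker-OMI-30 scenario.
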